### 6.2.2.6 Follow-Up of Subjects Reporting Adverse Events

All AEs must be reported in detail on the appropriate page of the eCRF and followed to satisfactory resolution, until the investigator deems the event to be chronic or not clinically significant, or until the subject is considered to be stable.

### 6.2.3 Clinical Laboratory Tests

Clinical laboratory tests will be performed at the visits indicated in the SOE (Table 13–1). After Screening, all visits that include laboratory tests must occur after an 8-hour fast. Sample collection (blood, urine) should be performed before FA and ICGA are performed. Sample collection, processing, and shipping should be performed according to the local laboratory requirements.

Routine laboratory tests will be evaluated by a central laboratory and will include the following:

- **Hematology**: hemoglobin, hematocrit, red blood cell count, white blood cell count with differential, mean corpuscular volume, mean corpuscular hemoglobin, mean corpuscular hemoglobin concentration, and absolute platelet count.

- **Serum chemistry:** total protein, sodium, potassium, calcium, chloride, inorganic phosphate, albumin, fasting blood glucose\*, glycated hemoglobin, total cholesterol, high-density lipoprotein and low-density lipoprotein† cholesterol, follicle-stimulating hormone, human chorionic gonadotropin (β-subunit), triglycerides, blood urea nitrogen, creatinine, uric acid, bilirubin (total and direct), alkaline phosphatase, aspartate aminotransferase, C-reactive protein, alanine aminotransferase, γ-glutamyltransferase, lactate dehydrogenase, and creatine kinase.
- **Urinalysis:** pH, glucose, ketones, specific gravity, nitrite, protein, bilirubin, urobilinogen, and blood. Microscopic urinalysis will be performed if urinalysis results are abnormal.

\*Fasting at Screening is not required; therefore, glucose testing at Screening may be fasting or nonfasting. All subsequent laboratory tests should be performed after an 8-hour fast (see SOE, Table 13–1).

†Low-density lipoprotein will be directly measured (eg, beta-quantification [ultracentrifugation]) if a subject's triglyceride level is  $\geq 400$  mg/dL.

**Serum pregnancy test:** Serum pregnancy testing will be performed for all females at Screening (Visit 1) and the EOS visit.

**Urine dipstick pregnancy test:** On Day 1, a urine pregnancy dipstick test will be performed for all females who are either premenopausal or have been postmenopausal for <1 year to confirm their eligibility for assignment to study treatment.

**Urine drug test:** A screen for drugs of abuse will be performed at Screening and Day 1 according to the local laboratory standard practices.

#### 6.2.4 Vital Sign Measurements

Vital sign measurements will be performed at the indicated visits in the SOE (Table 13–1). The following vital signs will be measured:

- Blood pressure (systolic and diastolic [mm Hg])
- Pulse (beats per minute)
- Body temperature (°C) (The method used to obtain a subject's body temperature at Screening should be used for that subject at all subsequent measurements)

- Height (cm) and body weight (kg). Height is to be measured at Screening only

Supine blood pressure, pulse, and body temperature (°C) will be recorded after the study subject has been recumbent and at rest for at least 5 minutes.

### **6.2.5 Physical Examination, Medical History, and Medication History**

A limited physical examination will be performed at the indicated visits in the SOE (Table 13–1). The limited physical examination includes a review of the subject’s medical history, medication history, and evaluation of relevant body systems complaints. In case of relevant findings, full evaluation of the condition needs to be conducted.

### **6.2.6 Electrocardiogram**

A standard 12-lead ECG will be performed at Screening to assess eligibility to participate in the study; a subsequent 12-lead ECG will be performed at the EOT visit (Table 13–1). All ECGs will be reviewed by the investigator, and any findings will be documented on the ECG eCRF page.

### **6.2.7 Demographics**

Demographics information will be collected at Screening as follows: age, race, iris color, and sex.

### **6.2.8 Eligibility**

Eligibility will be evaluated at Screening and on Day 1 using the criteria outlined in Section 4.1. Subjects must meet all inclusion and none of the exclusion criteria to be considered eligible for the study.

### **6.2.9 Clinical Significance of Safety Assessments**

Any abnormal laboratory test results (hematology, serum chemistry, or urinalysis) or other safety assessments (eg, vital sign measurements, ophthalmological assessments) — including those that worsen from Baseline — that are deemed to be clinically significant in the medical and scientific judgment of the investigator are to be recorded as AEs or SAEs.

However, any clinically significant safety assessments that are associated with the underlying disease, unless judged by the investigator to be more severe than expected for the subject’s condition, are not to be reported as AEs or SAEs.

### 6.3 Pregnancy

Female subjects of childbearing potential (defined in Inclusion Criterion 10 of Section 4.1.1) and male subjects are required to use effective contraception throughout the study.

Acceptable methods of contraception for female subjects include oral contraceptives, other hormonal contraceptives (vaginal products, skin patches, or implanted/injectable products), or mechanical products such as an intrauterine device or barrier methods (diaphragm, condoms, spermicides). Note: Female subjects who are actively practicing abstinence or who have a partner that is sterile (eg, vasectomy) will be permitted to participate in the study without contraception use.

The acceptable method of contraception for male subjects is the use of a condom plus spermicide. Note: Male subjects who are actively practicing abstinence or who have a partner that is sterile (eg, postmenopausal or undergone successful sterilization [both defined in Inclusion Criterion 10 of Section 4.1.1]) will be permitted to participate in the study without contraception use.

Pregnancy is not regarded as an AE unless there is a suspicion that an investigational product may have interfered with the effectiveness of a contraceptive medication. Any pregnancy that occurs during study participation must be reported using a clinical study pregnancy form. To ensure subject safety, each pregnancy must be reported to PPD/sponsor within 2 weeks of learning of its occurrence. The pregnancy must be followed up to determine its outcome (including spontaneous miscarriage, elective termination, normal birth, or congenital abnormality) and the health status of mother and child, even if the subject was discontinued from the study. Pregnancy complications and elective terminations for medical reasons must be reported as an AE or SAE. Spontaneous miscarriages and congenital abnormalities of the child must be reported as an SAE.

Any SAE occurring in association with a pregnancy, brought to the investigator's attention after study completion, and considered by the investigator as possibly related to the study treatment, must be promptly reported to PPD/sponsor.

### 6.4 Assessment of Plasma Concentrations of MT-0814 and Metabolites

Plasma concentrations of MT-0814 and its metabolites M5 and M6 will be assessed on Days 1, 29, 57, and 85 (EOT). The plasma concentration sample collection schedule is presented in Table 13–2; on each of the days specified above and in the table, a single predose and a single 2-hour postdose blood sample will be collected for these assessments.

Subjects will be instructed to refrain from taking their study drug on the mornings of these scheduled blood collection days, and instead will be instructed to bring those doses to the site so that they can be taken after predose blood samples are collected.

Plasma concentrations of MT-0814 and the metabolites M5 and M6 will be determined by [REDACTED] (Table 11–1). Comprehensive PK analyses of MT-0814 and its metabolites will be performed in future studies.

Plasma samples remaining from PK analysis may be retained by the sponsor for additional investigations (ie, long-term stability and/or reproducibility).

## **6.5 Review of Concomitant Medications**

Concomitant medication usage will be assessed at every visit starting at Day 1. Details for the recording of concomitant medications are in Section 5.8.1.

## **6.6 Dispensing of Study Drug**

Study drug will be dispensed at the study visits indicated in the SOE (Table 13–1). Details on the management of clinical supplies, including accessing IWRS and dispensing masked study drug, for the study are in Section 5.4.

## **6.7 Review of Subject Diary for Compliance**

Subject diaries will be reviewed for compliance by site staff at each study visit indicated in the SOE (Table 13–1). If compliance is suboptimal, the subject will be re-educated on the need to administer [REDACTED]

## **7 Statistical and Analytical Plan**

A study eye will be identified for each subject; refer to Section 4.1 for the definition of the study eye. The nonstudy eye will be referred to as the fellow eye.

Unless otherwise specified, efficacy will be summarized for the study eye only. Ocular safety summaries by eye will be presented for the study eye, the fellow eye, and the worse eye where the worse eye is the eye that has the most negative response between the study and fellow eye for a given assessment/visit.

### **7.1 Primary Efficacy Endpoint**

The primary efficacy endpoint is the change from Baseline (Day 1) in BCVA at Week 12.

### **7.2 Key Secondary Efficacy Endpoint**

The key secondary efficacy endpoint is the change from Baseline (Day 1) in CSFT at Week 12.

### **7.3 Other Secondary Efficacy Endpoints**

The following secondary efficacy endpoints will be assessed:

- Changes from Baseline (Day 1) in BCVA by visit.
- Changes from Baseline (Day 1) in CSFT by visit.
- Proportions of subjects who achieve dry retina (defined in Sections 3.1 and 6.1.2) at Weeks 4, 8, 12, and 16.
- Changes from Baseline (Screening) in total lesion area (assessed via FA, ICGA, and CFP) at Week 12.
- Changes from Baseline (Screening) in CNV area (assessed via FA, ICGA, and CFP) at Week 12.
- Changes from Baseline (Screening) in leakage area (assessed via FA, ICGA, and CFP) at Week 12.
- Changes from Baseline (Screening) in polyp area (assessed via FA, ICGA, and CFP) at Week 12.
- Proportions of subjects who require rescue therapy (Section 4.2.3).

- Duration of time from Baseline (Day 1) to initiation of rescue therapy (Section 4.2.3).
- Proportions of subjects whose BCVA scores have increased/decreased by 5, 10, or 15 letters from Baseline (Day 1) to Week 12.

## 7.4 Sample Size Calculations

The sample size for this study was not selected based on statistical power calculations, but rather on clinical considerations. Approximately 35 subjects will be randomly assigned (in a 3:3:1 ratio) to receive MT-0814 [REDACTED] MT-0814 [REDACTED] or placebo [REDACTED]. Randomization will be stratified by the BCVA score category (scores  $\leq 55$ , 56 to 70, or  $\geq 71$ ) observed for the subject's study eye on Day 1 (Baseline).

## 7.5 Analysis Sets

The following analysis sets will be used in the statistical analyses:

- Full-analysis set (FAS): The FAS will consist of all participants who were randomly assigned to receive double-masked study drug and who have received at least 1 dose of study drug. All analyses using the FAS will group participants according to randomly assigned treatment.
- Per-protocol set (PPS): The PPS will consist of all FAS participants who meet all of the inclusion criteria and none of the exclusion criteria, have at least 75% compliance with study treatment, have not taken any of the prohibited medications listed in Section 5.8.2, and have no significant protocol deviations. Subjects will not be excluded from the PPS if they discontinued treatment due to lack of efficacy or if they have protocol deviations, including unmasking, that are attributable to lack of efficacy. All analyses using the PPS will group participants according to treatment actually received.
- Safety set (SS): The SS will consist of all participants who received any study drug. All analyses using the SS will group participants according to the treatment that is actually received.
- MT-0814 plasma concentration data set: The PK data set will consist of plasma concentration data of samples obtained from all participants who received any active study drug.

The FAS and PPS will be used for the efficacy analysis with the primary population for analysis being the FAS. Safety will be summarized using the SS.

## 7.6 Description of Subgroups to be Analyzed

Efficacy summaries will also be presented for the following subgroups:

- CNV type (predominantly classic, minimally classic, occult with no classic type; refer to Section 6.1.3)
- Presence/absence of PCV (only if a sufficient number of subjects with PCV are assessed)
- Presence/absence of RAP (only if a sufficient number of subjects with RAP are assessed)
- BCVA at Baseline (Day 1)
- Age
- Sex
- Body mass index

## 7.7 Subject Demographics and Other Baseline Characteristics

Descriptive statistics will be provided by treatment group for subject demographics and all ocular and Baseline characteristics. Relevant medical history (ocular and nonocular) and current medical conditions will be tabulated by treatment group. Ocular summaries will be presented for the study eye and the fellow eye. Other relevant Baseline information will be listed and summarized as appropriate with descriptive statistics. Analyses will be based on the FAS, PPS, and SS.

## 7.8 Treatment Exposure and Compliance

As noted in Section 5.7, subjects will be asked to complete a daily diary noting each administration of study drugs and compliance will be calculated based on the diary data. Descriptive statistics will be provided to characterize study treatment exposure and compliance using the FAS, PPS, and SS. Duration of exposure will be calculated in days as the (date of last dose – date of first dose + 1). [REDACTED]

[REDACTED]

## 7.9 Statistical Analysis Methodology

Statistical analysis will be performed using SAS software Version 9.4 or higher. Continuous variables will be summarized using the mean, standard deviation, median, minimum value, and maximum value. Categorical variables will be summarized using frequency counts and percentages. Data will be listed in data listings.

Details of the statistical analyses, methods, and data conventions are described in the statistical analysis plan (SAP).

All statistical tests will be 2-sided and performed using a 5% significance level, leading to 95% (2-sided) confidence intervals. Pairwise comparisons will be performed with no multiplicity adjustments. Additionally, no multiplicity adjustments will be performed for multiple endpoints.

### 7.9.1 Analysis of Primary Efficacy Endpoint

The primary analysis will be performed on the study eye within the FAS. The following 2-sided hypothesis will be tested:

- H0: The difference in mean change from Baseline in BCVA in the study eye at Week 12 between placebo and MT-0814 is equal.
- Ha: The difference in mean change from Baseline in BCVA in the study eye at Week 12 between placebo and MT-0814 is not equal.

The primary analysis will be performed using an analysis of covariance (ANCOVA) model including fixed effect for treatment and Baseline BCVA score as a covariate. Subjects with missing data at Week 12 or who receive rescue therapy will have their data imputed by worst observation carried forward (WOCF) method. Only postbaseline observations observed prior to dropout or receipt of rescue therapy (whichever occurs first) will be carried forward. Additional sensitivity analyses such as the following may be performed:

- An ANCOVA on observed data
- A t-test on observed data
- The mixed models repeated measures (MMRM) including observed data for all visits through Week 12

- The ANCOVA at Week 12 incorporating data from the fellow eye with missing data at Week 12 imputed using WOCF. (This analysis will be dependent on the number of subjects who have both eyes meet all entry criteria.)
- Multiple imputations of missing data analyzed using the same ANCOVA model as for the primary analysis.

Analysis will be performed separately to compare each dose of MT-0814 to placebo (eg, including only subjects receiving placebo and subjects receiving the MT-0814 dose being compared to placebo.)

The change from Baseline in BCVA at Week 12 will be also be descriptively summarized by the subgroups presented in Section 7.6. Statistical hypothesis testing to compare each MT-0814 dose to placebo within subgroups will be performed by t-test if the subgroup size is sufficient.

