**Primary Endpoint**

The primary endpoint is the assessment of change from Baseline in BCVA (via ETDRS) at Week 12. A 2-sided hypothesis will be tested: whether the change from Baseline to Week 12 in BCVA between MT-0814 and placebo are equal or not equal. The primary analysis will be performed using an analysis of covariance (ANCOVA) model including fixed effect for treatment and Baseline BCVA score as a covariate. Subjects with missing data at Week 12 or who receive rescue therapy will have their data imputed by worst observation carried forward method. Only postbaseline observations observed prior to dropout or receipt of rescue therapy (whichever occurs first) will be carried forward. Additional sensitivity analyses may be performed.

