### 3.1.1 Rationale for Study Design

This Phase 2a study has a double-masked, randomized, multicenter, placebo-controlled, parallel-group design. The study will evaluate the safety, tolerability, efficacy, and PK of [REDACTED] MT-0814 administration for the treatment of subjects with AMD. [REDACTED]

[REDACTED] given this fact, and given that this is a small, proof-of-concept study to detect whether MT-0814 is effective against the signs and symptoms of AMD, it is considered appropriate to compare the study

drug against a placebo. Subjects who participate in this study will be examined on a weekly basis, and rescue therapy (via anti-VEGF injection; refer to Section 4.2.3 for details) will be provided in the event that further disease-related deterioration is observed.

[REDACTED]

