### **4.2.3 Treatment Failure and Initiation of Rescue Therapy**

In case the investigator considers that the ocular condition is worsening to an extent that the subject needs rescue medication, the subject will be considered a treatment failure.

Investigators should discontinue administration of study drug and begin rescue therapy with intravitreal injections of an anti-VEGF agent (aflibercept or ranibizumab) per standard of care if a subject exhibits any of the following:

- Increase in retinal/subretinal hemorrhage or new retinal/subretinal hemorrhage from Screening for which the investigator deems rescue therapy is necessary.
- Emergence of new retinal/subretinal fluid, increase in retinal/subretinal fluid, or cystoid macular edema from Day 1 for which the investigator deems rescue therapy is necessary.
- Decrease in BCVA of  $\geq 10$  letters from Day 1 that is related to disease activity.
- Any other reason that, in the investigator's opinion, requires discontinuation of study drug and initiation of rescue therapy.

All EOT evaluations need to be completed at the time that treatment failure has been declared.

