#### 6.1.1 Visual Acuity via Early Treatment of Diabetic Retinopathy Study

The BCVA of each subject will be assessed via the ETDRS without pupil dilation as indicated in the SOE (Table 13–1). The BCVA will be assessed for both the study and fellow eye of each subject at Screening, Day 1, the EOT visit, and the EOS visit. At all other visits, BCVA will be assessed for the study eye only. Refer to the *MT-0814 Ophthalmology Procedure Manual* for detailed instructions on BCVA-ETDRS assessment.

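### The primary WOCF rule leaves Baseline out, so an early treatment failure can be scored as a BCVA gain while a stable subject who misses only Week 12 is scored as a loss

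*Combined protocol and SAP*

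**What the plan says.** Section 7.1 defines the endpoint: "The primary efficacy endpoint is the change from Baseline (Day 1) in BCVA at Week 12". Section 7.9.1 gives one rule for two different situations: "Subjects with missing data at Week 12 or who receive rescue therapy will have their data imputed by worst observation carried forward (WOCF) method". It then limits what may be carried: "Only postbaseline observations observed prior to dropout or receipt of rescue therapy (whichever occurs first) will be carried forward". The synopsis repeats both sentences.

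Three other places determine how the rule behaves.

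- **Number of readings.** Section 3.1.1 states: "Subjects who participate in this study will be examined on a weekly basis". Section 6.1.1 and Table 13-1 have study-eye BCVA measured at each of these visits.
- **Who counts as a failure.** Section 4.2.3 treats every subject who needs rescue as a treatment failure. Only one of its four triggers is a BCVA loss (10 letters or more, related to disease activity). The others are hemorrhage, fluid or edema ("cystoid macular edema from Day 1 for which the investigator deems rescue therapy is necessary"), and any other reason in the investigator's opinion. EOT assessments are due when failure is declared.
- **Who is analysed.** The FAS in Section 7.5 needs randomization and subjects "who have received at least 1 dose of study drug". It does not require a post-Baseline reading.

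The sensitivity analyses in Section 7.9.1, multiple imputation among them, are optional. Section 7.9.2 applies WOCF to CSFT but does not say whether Baseline may be carried.

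**The concern.** WOCF is normally chosen because it is conservative. As written here, its direction depends on when and why the data stop. The worst of several noisy readings falls as readings accumulate, so the rule is mild for a subject who fails after one or two visits and severe for a subject who attends eleven visits and misses the twelfth.

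Two results follow. A subject whom Section 4.2.3 calls a treatment failure can count as a vision gain in the primary analysis. A subject whose vision has not changed can count as a loss because of one missed visit. Placebo is planned at 5 subjects, so a single imputed value carries one fifth of that arm's mean. There is also a gap: a FAS subject with no eligible post-Baseline reading has nothing to carry, and no rule is given.

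**Working it through.** The plan states no expected imputed value, BCVA SD or power figure, so there is nothing of its own to reproduce beyond the allocation: 35 subjects at 3:3:1 gives 15, 15 and 5, as in Section 3.1.

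**Inputs from the documents.** Weekly BCVA; Baseline not carried; a subject missing only Week 12 has k = 11 readings (Weeks 1 to 11); a subject rescued after the first visit has k = 1.

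**Assumptions.** A stable eye, normal visit-to-visit noise with within-subject SD s, and independent visits unless stated. The range used is s = 2 to 6 letters.

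**1. Early failure scored as a gain.** The score is a gain only if all k readings exceed Baseline. With k + 1 exchangeable readings, the chance that Baseline is the lowest is 1/(k + 1), whatever s is:

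- k = 1: 1/2 = 50%
- k = 2: 1/3 = 33%
- k = 3: 1/4 = 25%

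With scores rounded to whole letters and s = 3 to 5, the chance of a gain of at least 1 letter is 45-47% for k = 1 and 29-31% for k = 2. If true acuity is already 5 letters down, a single reading still shows such a gain in 10-22% of cases. For a failure declared on the 10-letter criterion this cannot happen: the qualifying drop is itself a pre-rescue post-Baseline reading and is carried.

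**2. Stable subject missing only Week 12.** The expected score is E[min of k standard normals] × s. For k = 11 the factor is -1.586:

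| s (letters) | 2 | 3 | 4 | 5 | 6 |
|---|---|---|---|---|---|
| Expected score | -3.2 | -4.8 | -6.3 | -7.9 | -9.5 |

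With first-order autocorrelation of 0.5 between visits, s = 3, 4 and 5 give about -4.3, -5.7 and -7.1. With 0.7 they give about -3.7, -5.0 and -6.2. Among simulated subjects who never show a 10-letter drop, the mean is about -4 to -5 for s = 3 to 6 with independent noise. At s = 2 such drops hardly occur, and the figure stays near -3.2.

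**3. Effect on an arm mean.** One such subject at s = 4 to 5 moves the placebo mean by 6.3/5 = 1.3 to 7.9/5 = 1.6 letters, and an active mean by 6.3/15 = 0.4 to 7.9/15 = 0.5. Over s = 2 to 6, the placebo shift runs from 3.2/5 = 0.6 to 9.5/5 = 1.9.

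**4. What carrying Baseline changes.** With Baseline eligible, the expected score for a stable rescued eye uses k + 1 readings: a factor of -0.564 for k = 1 and -1.629 for k = 11. At s = 4 to 5 that is -2.3 to -2.8 after one visit and -6.5 to -8.1 after eleven. The spread between the two cases falls from 1.586 × s to (1.629 - 0.564) × s = 1.065 × s. It narrows but does not vanish.

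**The case against.** The strongest reply is that the endpoint is BCVA, so a pre-rescue reading above Baseline is observed vision and not an error. Failure also has its own endpoints in Section 7.3: the proportion rescued and the time to rescue. That stands as far as it goes, and capping the change at 0 does build part of a failure score into a vision endpoint. But the primary rule already departs from observed vision by taking the worst value, and an imputation meant to be unfavourable should not return a gain for a declared failure.

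It may also be said that the listed sensitivity analyses and the SAP settle the matter. The analyses are optional. Section 7.9 leaves data conventions to a SAP whose separate text is not among the documents reviewed, and Section 7.9.1 already fixes the carry-forward rule.

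Several stronger readings are tempting but are not supported:

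- **A fixed penalty of 6 to 8 letters for one missed visit.** That needs an SD of about 3.8 to 5.0 and independent noise, and the documents give neither.
- **A bias towards one arm.** The documents give no rescue rates by arm, and any share of rescued placebo subjects scored as gains would rest on invented inputs. If early rescue were more common on placebo, lenient scoring of it would work against MT-0814.
- **The same Baseline exclusion for CSFT.** Section 7.9.2 does not contain that restriction; it is silent.
- **A frequent problem with empty records.** EOT assessments are required at failure and, by footnote b of Table 13-1, at early withdrawal, so few subjects should lack a reading.

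Finally, the leverage of one value in an arm of 5 comes from the sample size, not from WOCF. The study is a small proof of concept and was not sized on power.

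**Conclusion.** The point holds in a limited form. On the text, a subject declared a treatment failure early, on a trigger other than the 10-letter loss, can be scored as a BCVA gain. For a stable eye with independent noise the chance is 50%, 33% and 25% after 1, 2 and 3 readings. A stable subject who misses only Week 12 is expected to be scored as a loss. Its size is an assumption, about -3 to -9.5 letters over an SD of 2 to 6, but its direction is the same throughout that range and under the visit correlations tried. The missing rule for a FAS subject with nothing to carry is a real but minor gap. This is worth correcting because the change is cheap. It does not show that the trial's comparison is biased in a known direction.

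**What to change.** 1. **Rescued or treatment-failure subjects.** In Section 7.9.1 and the synopsis, carry forward the worst of Baseline and all pre-rescue values, so that the BCVA change cannot exceed 0. This alters a score only when every pre-rescue reading is above Baseline or none exists.
2. **CSFT.** State the same rule in Section 7.9.2, so that the CSFT change for these subjects cannot fall below 0.
3. **Week 12 missing without rescue.** Change the multiple imputation with the same ANCOVA from optional to a mandatory, pre-specified sensitivity analysis reported beside WOCF. It also gives a value to FAS subjects with no post-Baseline reading.

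The cost is a few sentences in the protocol and SAP, with no new data or visits. No change to the rescue criteria is proposed. There are two downsides. The rescue rule becomes a partial failure score and still depends somewhat on the number of readings (step 4 of the working). Multiple imputation will be imprecise with 5 placebo subjects, which is why it is proposed beside WOCF and not in its place.

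### The optional fellow-eye ANCOVA at Week 12 has no term for the correlation between two eyes of one subject, so if eyes are entered as separate records its type I error exceeds 5%

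*Combined protocol and SAP*

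**What the plan says.** The primary comparison is on one eye per subject: "The primary analysis will be performed on the study eye within the FAS". Its ANCOVA is described as "including fixed effect for treatment and Baseline BCVA score as a covariate". Section 7.9.1 then introduces a list with "Additional sensitivity analyses such as the following may be performed", and one item is "The ANCOVA at Week 12 incorporating data from the fellow eye with missing data at Week 12 imputed using WOCF". A condition is attached: "This analysis will be dependent on the number of subjects who have both eyes meet all entry criteria". No threshold number is given, and the item does not say how the second eye enters the model. Section 7.9 refers to an SAP for detail, but the document contains no further text on this analysis.

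On the error rate, Section 7.9 says "All statistical tests will be 2-sided and performed using a 5% significance level" and "Pairwise comparisons will be performed with no multiplicity adjustments". Section 3.1 plans 15, 15 and 5 subjects, and Section 7.9.1 compares each dose with placebo separately, so each comparison is 15 v 5.

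On the data available, Section 6.1.1 schedules BCVA in both eyes at Screening, Day 1, the EOT visit and the EOS visit. For the rest it says "At all other visits, BCVA will be assessed for the study eye only". Table 13–1 has a BCVA assessment every week.

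**The concern.** Randomization is by subject, so the subject is the independent unit for comparing treatments. A second eye from the same subject adds some information, but less than a new subject would if the two eyes' outcomes move together. A model with treatment and Baseline only counts every eye as a full unit. It therefore understates the standard error and uses too many residual degrees of freedom. With five placebo subjects per comparison, counting some of them twice matters.

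The purpose of the analysis is to show whether the primary result stands when qualifying fellow eyes are added. If its interval is too narrow, it can appear to confirm a result that the data do not support. It is to be run when enough subjects have two qualifying eyes, which is also when the understatement is larger.

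A second matter is comparability of the imputed values. One WOCF rule is written, but the visit schedule gives the two eyes very different material for it.

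**Working it through.** **Inputs from the documents.** Two-sided level 5%, no multiplicity adjustment (Section 7.9); 15 v 5 subjects per comparison (35 × 3/7 = 15; 35 × 1/7 = 5; Section 3.1); treatment and Baseline BCVA in the model (Section 7.9.1).

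**Assumptions, because the documents give no figure.** Share f of subjects with two qualifying eyes; between-eye residual correlation ρ; normal residuals; equal variance in both eyes; bilateral status unrelated to arm; no treatment effect.

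**Step 1: reproduce the plan's 5%.** A simulated ANCOVA on one eye per subject, 15 v 5, 100,000 runs per setting, rejects in 4.9% to 5.2% of runs. Stacking both eyes with ρ = 0 gives 4.9% to 5.1%. The nominal level is recovered when records really are independent.

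**Step 2: stacked eyes with ρ > 0.** Per subject there are 1 + f records on average, and a share f of subjects adds a covariance term 2ρ. The true variance of the treatment contrast is therefore inflated by

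design effect = 1 + 2fρ/(1 + f),

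and the large-sample error rate is 2 × [1 − Φ(1.96/√design effect)].

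Example, f = 0.2 and ρ = 0.4: 1 + 0.16/1.2 = 1.133; 1.96/√1.133 = 1.84; error rate 6.6%. Simulation of the same setting gives 6.4%.

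Over ρ = 0.3 to 0.7:

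| Bilateral share f | Design effect | Error rate, formula | Error rate, simulation 15 v 5 |
|---|---|---|---|
| 10% (2 of 20 subjects) | 1.055 to 1.127 | 5.6% to 6.5% | 5.6% to 6.1% |
| 20% (4 of 20) | 1.100 to 1.233 | 6.2% to 7.8% | 6.0% to 7.7% |
| 40% (8 of 20) | 1.171 to 1.400 | 7.0% to 9.8% | 6.9% to 9.7% |
| 100% (20 of 20) | 1.300 to 1.700 | 8.6% to 13.3% | 9.0% to 14.1% |

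Over the wider range ρ = 0.2 to 0.8, simulation gives 5.2% to 6.6% at 10%, 5.7% to 8.0% at 20%, 6.2% to 10.5% at 40% and 7.4% to 15.1% at 100%. The model standard error divided by the true one runs from 0.99 (f = 0.1, ρ = 0.2) down to 0.73 (f = 1.0, ρ = 0.8).

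**Step 3: one record per subject.** Averaging the two eyes where both qualify gives 4.9% to 5.1% for every f from 0.1 to 1.0 and every ρ from 0 to 0.8 tried.

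**Step 4: does WOCF add to the inflation?** In a separate simulation (40,000 runs per setting, within-eye visit correlation 0.7 assumed), the study eye took its worst weekly value before dropout and the fellow eye took its single exit value or was absent.

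- ρ = 0, equal dropout of 20% or 40% in both arms: error rate 4.7% to 5.3%, standard error ratio 0.99 to 1.01. No inflation.
- ρ = 0.4, equal dropout: 5.9% to 9.4%, no higher than about the same settings without dropout (6.4% to 9.8%).
- ρ = 0, dropout 20% v 50%: 5.5% to 6.6%. The study-eye-only WOCF ANCOVA shows much the same (6.0% to 6.4%), so this is not specific to the fellow eye.

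**Step 5: how differently WOCF acts on the two eyes.** A study eye seen every week up to Week 11 has 11 postbaseline values to choose from. A fellow eye has at most one up to EOT. The expected minimum of 11 independent standard normal values is −1.59 SD. With equal within-eye visit correlation r this shrinks by √(1 − r): 1.59 × √0.5 = 1.12 SD at r = 0.5, and 1.59 × √0.3 = 0.87 SD at r = 0.7. These are upper figures, since earlier dropout leaves fewer values, and they apply only to imputed subjects.

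**The case against.** The strongest objection is that stacking is inferred. The item says only that fellow-eye data are incorporated, and an ANCOVA on the mean of the two eyes would also fit those words and hold 5%. The quoted model terms belong to the primary analysis, which has one eye per subject and needs no subject effect. The multiple-imputation item in the same list refers back to the primary model explicitly; the fellow-eye item does not. All this is correct, so a reader should not infer that the plan declares the eyes independent. What stands is that adding second-eye data to the only defined ANCOVA is the natural reading, and that averaging would redefine both outcome and covariate, which nothing in the text does.

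Second, the bilateral share may be small. Planned anti-VEGF injection in the fellow eye is an exclusion, a need for it during the study leads to discontinuation, and Section 6.1.3 provides angiography for the study eye only although inclusion criterion 3 relies on it. This makes the top of the range unlikely. It does not remove the problem at the shares for which the analysis would be thought worth running.

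Third, the analysis is optional, in a proof-of-concept study not sized for power. That limits the consequence, but does not make the interval right if the analysis is reported.

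A reader might also infer that the unequal effect of WOCF is part of the reason for the small standard errors. Step 4 shows that it is not under equal dropout. Nor are there two imputation rules; there is one rule and an unequal visit schedule.

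**Conclusion.** The point holds conditionally. If qualifying fellow eyes are added as separate records to the ANCOVA as defined, and the two eyes are positively correlated, standard errors are too small and the error rate exceeds 5%: about 6% at a 10% bilateral share, 6% to 8% at 20%, 7% to 10% at 40%, and 9% to 14% if every subject contributes both eyes. These figures rest on an assumed correlation of 0.3 to 0.7 and on the stated normality and equal-variance assumptions. At zero correlation there is no inflation.

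The WOCF matter is separate. It makes imputed values in the two eyes non-comparable and leaves a fellow eye without an exit value uncovered, but it is not a cause of the type I error. The 5% level of the primary test is unaffected, because that test uses the study eye alone. The change is worth making before the analysis is run, but nothing in the primary plan depends on it.

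**What to change.** Add a sentence to Section 7.9.1, or to the SAP, choosing one of two forms:

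- one record per subject, using the mean change over the eligible eyes with the mean Baseline of the same eyes; or
- an eye-level Week 12 model with eye-specific Baseline and a random subject intercept, using Kenward-Roger degrees of freedom.

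The first is simpler, and with only a few bilateral subjects per comparison the second has little data from which to estimate the between-eye correlation. State also the number of bilateral subjects at which the analysis will be run.

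For missing data, keep the primary WOCF rule for the study eye, and state that the fellow eye contributes only its EOT value and is left out if it has none. Replacing WOCF by observed values in both eyes is not needed. It would also change the study-eye handling of dropout and rescue, so a difference from the primary result could no longer be put down to the added eyes. An observed-data ANCOVA is already on the list.

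The cost is a few lines of text and code and no new data. The interval becomes wider, as it should: at a 20% bilateral share the stacked model's standard error is about 0.97 to 0.90 of the true one (ρ = 0.2 to 0.8), so a correct interval is wider by a factor of roughly 1/0.97 = 1.03 to 1/0.90 = 1.11.
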